10.3 Other study parameters

Comparison between immunological profiles of hospitalized children with COVID-19 and other cohorts (eg adults with severe COVID-19, non-admitted children with COVID-19) will be done using parametric (ANOVA) or non-parametric (Kruskal-Wallis) tests were applicable, depending on whether the data is normally distributed or not. Logistic regression will be used to determine associations between clinical parameters and the results from the questionnaires on Quality of Life and functioning.

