4.4 Sample size calculation

A formal sample size calculation cannot be done, since it is currently unknown what the variation in immunological response is children with COVID-19 or MIS-C and how this relates to outcome measures. Based on the number of participating sites and the inclusion rate in the first wave of the epidemic, we expect to be able to include at least 60 children in total, and 30 children for the immunological part of the study.

We expect the rate of consent for blood withdrawal to be higher in patients with more severe disease (since the blood can be taken during routine blood withdrawal and no separate venapuncture will be needed). Therefore, based on inclusion rates for the related COPP-study, we estimate we will be able to include at least 10 patients with MIS-C, 10 patients with moderate to severe COVID-19 and 10 patients with mild COVID-19. Clinical information will be available for all of the patients included in the immunological part of the study.

If we will have reached 60 inclusions for the immunological part of the study within the first 18 months of the study, we will do an interim analysis to determine if more inclusions are needed. Since this is an exploratory study, no formal maximal number of inclusions can be given, but based on previous inclusions in de COPP-study and the expected course of the epidemic we do not expect to reach a higher inclusion than 60 in this timeframe.

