8.1.1 Main study parameter/endpoint

For the clinical observational part of the study (analyzed together with data from the COPP-study) the main study parameters are:

- To describe the clinical features of the COVID-19 in hospitalized and outpatient pediatric patients in the Netherlands.
- To describe the clinical course of the COVID-19 in hospitalized and outpatient pediatric patients.
- To describe the response to treatment, including supportive care.
- To determine risk factors for severe disease in children with COVID-19.

For the immunological part of the COPP-IMM study, we will obtain a detailed immunological profile of children presenting to Dutch hospitals with acute SARS-CoV-2 infection or with a SARS-CoV-2 related post-infectious inflammatory syndrome. Since clinically relevant pediatric COVID-19 is rare and we will have a limited amount of material available from each patient, we will do this in a two-tiered approach. This will enable us to choose which will be the most informative in-depth immunological analysis following a more general screening of the innate and adaptive immune system.

In the FIRST TIER we will do a general assessment of the immune system. In this general assessment we will do the following investigations:

1. Detailed phenotypical analysis of the cells of the innate and adaptive immune system using multicolor flow cytometry. We will use the EuroFlow protocol PID Orientation

tube to be able to identify and quantify the main leukocyte and lymphocyte subsets, using 12 markers: CD27, CD45RA, CD8, IgD, CD16, CD56, CD4, IgM, CD19, CD3, CD45, and TCR $\gamma\delta$. This will enable us to identify B-cells (including B-cell subsets), T-cells (including T-cell subsets), NK-cells, monocytes (including non-classical CD16+ monocytes), dendritic cells, basophils, neutrophils and eosinophils (minimum of 4 mL of EDTA needed).

2. Multiplex analysis of inflammatory cytokines in serum using Luminex bead arrays (in excess of 100 analytes, to determine Th1/Th2 and innate responses) (200-400 uL).
3. Quantitative and qualitative (affinity) analysis of anti-SARS-CoV-2 antibodies in serum and potential cross-reactive antibodies to other coronaviruses (200-400 uL).

Depending on the results of the investigations in the first tier, we will choose one of the following in-depth immunological analyses for the SECOND TIER:

[figure not shown]

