10. STATISTICAL ANALYSIS

10.1 Primary study parameter(s)

Statistical analysis of the primary objective: immunological profiling of children with COVID-19 or MIS-C:

1. Relative distributions of immune cell subsets will be obtained by multicolor flow cytometry. Data will be imported in R for statistical analysis. Cytosplore will be used for clustering and dimensionality reduction (9). Distributions will be compared to available reference values (normal distribution of immune cell subsets in children, adjusted for age) and will be compared across subgroups (mild COVID-19, moderate to severe COVID-19 and MIS-C).
2. Cytokine levels will be analyzed in R and SPSS. Levels will likely be non-normally distributed, in which case non-parametric Kruskal-Wallis tests will be done for comparison across groups. To adjust for multiple testing, we will use the two-stage step-up method of Benjamini *et al* (10). Cytokine levels will be compared to normal values as already available for healthy adults, and across the subgroups(mild COVID-19, moderate to severe COVID-19 and MIS-C).
3. Levels of neutralizing antibodies will be compared across subgroups (mild COVID-19, moderate to severe COVID-19 and MIS-C) using ANOVA in SPSS.

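### The test choice in section 10.3 depends only on normality and ignores unequal variance, so comparisons with outside cohorts of a different size may miss the nominal error rate in either direction

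*Protocol*

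**What the plan says.** Section 10.3 covers comparisons of the immunological profiles of admitted children with "other cohorts (eg adults with severe COVID-19, non-admitted children with COVID-19" and similar groups. Section 8.1.3 describes the same aim, with an adult study and paediatric population-based studies as sources. The method in 10.3 is "parametric (ANOVA) or non-parametric (Kruskal-Wallis) tests were applicable, depending on whether the data is normally distributed or not". Nothing is said about unequal variance, the scale of analysis (raw or log), how normality is judged, or whether the choice is made per analyte or for a whole panel.

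Other passages bear on this:

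- Section 4.4 gives no formal sample size because "it is currently unknown what the variation in immunological response is". It expects "at least 10 patients with MIS-C, 10 patients with moderate to severe COVID-19 and 10 patients with mild COVID-19". The sizes of the outside cohorts appear nowhere.
- Section 8.1.1 describes a cytokine panel "in excess of 100 analytes".
- Section 10.1, item 2, on cytokines across the study's own subgroups, says "Levels will likely be non-normally distributed, in which case non-parametric Kruskal-Wallis tests will be done for comparison across groups", and for multiplicity "we will use the two-stage step-up method of Benjamini".
- Section 10.2 names Kruskal-Wallis without condition for secondary objectives 2 and 3, and section 10.1, item 3, names ANOVA without condition for neutralizing antibodies.

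**The concern.** With groups of unequal size, classical ANOVA is far more sensitive to unequal variance than to moderate non-normality. The rule in 10.3 looks at the second and not the first. Cohorts assembled in different studies, one of them in adults, have no design feature that makes their sizes or spreads equal.

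If the smaller cohort is the more variable, the rule will declare cohort differences that are not there. If the larger cohort is the more variable, it will miss real ones.

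A second effect depends on how the rule is read. If normality is judged per analyte, analytes with similar skewness would be divided between a test of means and a test of ranks. Their results could then not be set side by side across one panel.

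**Working it through.** **Inputs.** From the protocol: the rule (10.3), expected subgroups of about 10 (4.4) and unknown variation (4.4). Assumed, because the protocol is silent: a 5% level, outside-cohort sizes, and SD ratios from 1 to 3. The protocol states no error rate, so there is no figure of its own to reproduce.

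**Step 1: the mechanism.** For two groups, ANOVA is the pooled-variance t-test. Compare the true variance of the mean difference, V = s1²/n1 + s2²/n2, with what the pooled test uses on average, P = [((n1−1)s1² + (n2−1)s2²)/(n1+n2−2)] × (1/n1 + 1/n2).

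- 10 v 30, SDs 2 and 1 (smaller group more variable): V = 4/10 + 1/30 = 0.433; P = (36 + 29)/38 × 0.1333 = 0.228; V/P = 1.90. The effective critical value is 2.024/√1.90 = 1.469, and the two-sided normal tail is about 14%.
- 10 v 30, SDs 1 and 2 (larger group more variable): V = 1/10 + 4/30 = 0.233; P = (9 + 116)/38 × 0.1333 = 0.439; V/P = 0.532. The effective critical value is 2.024/√0.532 = 2.775, with a tail of about 0.6%.
- Equal sizes: V = P whatever the SDs, so the rate stays near nominal.

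**Step 2: simulation of the rule.** Normal data with equal means, 2,500 runs per scenario. The rule was coded as Shapiro-Wilk at 5% in each group, then ANOVA if both groups pass and otherwise Kruskal-Wallis. The protocol names no check, so this coding is also an assumption. The table gives the percentage of runs with p < 0.05.

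| Sizes | SD ratio | Rule, smaller group more variable | Rule, larger group more variable |
|---|---|---|---|
| 10 v 30 | 1.5 / 2 / 3 | 9.5 / 15.7 / 22.1 | not listed / 0.9 / 0.5 |
| 20 v 30 | 1.5 / 2 / 3 | 7.0 / 8.3 / 11.5 | 3.3 / 3.3 / 2.6 |
| 20 v 40 | 1.5 / 2 / 3 | 9.2 / 12.1 / 14.5 | 2.7 / 1.8 / 1.4 |
| 30 v 60 | 1.5 / 2 / 3 | 9.3 / 10.2 / 13.4 | 2.5 / 1.7 / 1.9 |
| 30 v 100 | 1.5 / 2 / 3 | 10.0 / 15.5 / 21.6 | 1.8 / 0.8 / 0.4 |

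With equal SDs the rule gives 4.2% to 5.8% at all sizes. With equal sizes (10 v 10 to 30 v 30) and SD ratios up to 3 it gives 5.0% to 7.2%, or up to about 8% if normality is checked on pooled residuals.

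**Step 3: what causes it.** At 10 v 30 with SD ratio 2, ANOVA without any pre-test gives 15.9%, against 15.7% for the rule. Kruskal-Wallis alone, read as a test of location, gives 10.5% there and 12.8% at ratio 3. The two-group Welch test gives 4.0% to 6.1% in every normal scenario. Brunner-Munzel, run at 10 v 40 and 20 v 60 with ratios 1.5 to 2, stays at 4% to 6%.

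**Step 4: the split between tests.** For log-normal data with 10 per group, all groups pass Shapiro-Wilk in 77%, 57% and 14% of runs at log-SD 0.3, 0.5 and 1.0. The check therefore sorts skewed analytes partly by chance.

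**Step 5: power.** At 10 v 10 with a shift of one log-SD, power is 57% for the two-stage rule and 56% for log-scale Welch.

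**The case against.** The strongest reply is that this is detail for a statistical analysis plan, which is not shown, and that the word ANOVA does not rule out Welch's form. In part that stands: the normality check, the scale and the variance handling could all be settled there. But 10.3 does not leave the choice open. It states a rule and names its single criterion, and that criterion does not address the condition that matters most for cohorts of unequal size.

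It is also fair that nothing in the protocol shows which cohort will be larger or more variable. One could argue that unequal variance must be expected because the children span all severities while the adults are severe. The text does not support that: 10.3 compares admitted children, who are themselves a selected group. What can be said is only that equal variance cannot be presumed.

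A reader might infer that choosing the test from the data is itself what inflates the error. Steps 2 and 3 show otherwise. A reader might also infer that one panel will certainly be tested by two methods. The rule speaks of the data as a whole, and choice per analyte is the likely reading but not a stated one.

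Finally, the weight is low. Section 4.4 says "Since this is an exploratory study, no formal maximal number of inclusions can be given", and 10.3 is the lowest tier of analysis.

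**Conclusion.** The point holds as a minor one. The rule in 10.3 conditions on normality and takes no account of unequal variance. For 10 v 30 and 30 v 100 with SD ratios of 1.5 to 3, its false-positive rate is about 10% to over 20% when the smaller cohort is more variable and about 0.5% to 2% when the larger one is. A milder imbalance such as 20 v 30 gives smaller departures, and equal sizes or equal SDs leave the rate at about 4% to 7%.

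These figures depend on the assumed sizes, SD ratios, 5% level and normal data. No single percentage should be read as a property of this protocol or as an upper bound: at 10 v 60 with SD ratio 3 the same simulation gives 31.3%.

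The point does not carry over to the primary cytokine analysis in 10.1, item 2. Kruskal-Wallis is already expected there, with false-discovery control, in groups of about 10/10/10 where the imbalance mechanism is weak.

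**What to change.** In 10.3, replace the choice that depends on normality by one method fixed in advance for all analytes: Welch's unequal-variance test (Welch ANOVA for more than two groups) on log-transformed levels, reported as a geometric mean ratio with a 95% interval. If a rank method is preferred for two-group comparisons, use Brunner-Munzel. The log scale must be fixed together with the test: on raw log-normal data with equal medians and unequal log-SDs, Welch gave 8.5% at 20 v 40, because the means then differ. Removing the normality check but keeping classical ANOVA or Kruskal-Wallis would not be enough.

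Making Kruskal-Wallis unconditional in 10.1, item 2, is optional.

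The cost is a change of wording. The methods are available in R, which the protocol already uses, and the power comparison shows no material loss. There are two small downsides: estimates are on a log scale, and values below the detection limit need a stated handling.

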11. ETHICAL CONSIDERATIONS

11.1 Regulation statement

This prospective cohort study is subject to the Medical Research Involving Human Subjects Act (WMO). This study will be conducted according to the principles of the Declaration of Helsinki (version 2013, 19-10-2013, (www.wma.net)) and in accordance with the Medical Research Involving Human Subjects Act (WMO), the General Data Protection Regulation (AVG), the Dutch Act on implementation of the General Data Protection Regulation (uitvoeringswet AVG) and other guidelines, regulations and acts. We will comply with the principles enshrined in the Council of Europe Convention on human rights and biomedicine – known as the Bioethics Convention Oviedo). Its main purpose is to protect individuals against exploitation.

11.2 Recruitment and consent

The recruitment and informed consent procedures will be done by local researcher in the hospital. Local researchers will be recorded in a researcher log. Subjects will be approached for consent preferably within at least 24h after presentation in the hospital. They will have at least 24h to consider their decision. This time facilitates the subject to make a considered decision, yet will ensure reliable prospective data collection.

Both parents/caregivers need to sign the consent form before the child can be included in the study. In case only one parent is present during the hospital visit/hospitalization (for example, due to COVID-19 restrictions), is it obligated to collect the second signature as soon as possible. This can be done, for example:

- During the next time the second parent visits the hospital,
- By sending the patient information and the consent form to the second parent; the signed form can be returned with a reply envelop,
- The second parent returns a signed consent form by e-mail.

In case of study subjects age 12-16 years of age, we will require their written consent, as well as at least one parent or caregiver.

In case of study subjects age 16 and older, we will only require their written consent and not from their parents or caregivers.

See attachment for patient information letter and informed consent.

11.3 Objection by minors or incapacitated subjects (if applicable)

The research will be conducted according to the Code of Conduct for Medical Research by the Federation of Dutch Medical Scientific Societies (Federa) and the code of conduct relating to expressions of objection by minors participating in medical research by the Netherlands Association for paediatric research.

(<https://www.ccmo.nl/onderzoekers/publicaties/publicaties/2001/06/01/gedragscode-verzet-bij-minderjarigen>).

<https://english.ccmo.nl/investigators/legal-framework-for-medical-scientific-research/codes-of-conduct/code-of-conduct-for-medical-research>

11.4 Benefits and risks assessment, group relatedness

Subjects do not benefit personally from study participation. This non-therapeutic research with minors will have negligible risks and minimal burden. This study can only be performed in minors, as it will provide age-specific data that cannot be obtained otherwise.

11.5 Compensation for injury

The sponsor/investigator has a liability insurance which is in accordance with article 7 of the WMO.

We request dispensation by the METC for the statutory obligation to provide insurance for damage to research subjects, because participating in this study is without risks.

12. ADMINISTRATIVE ASPECTS, MONITORING AND PUBLICATION

12.1 Handling and storage of data and documents

Patients will receive a COPP-IMM study number. The key to the code is safeguarded by the research team at the local site, by placing this in a secured datasafe managed by the 'Trialbureau' of the 'Willem-Alexander Kinderziekenhuis' (WAKZ).

Documentation belonging to the study will be archived for 15 years in the "Investigator File". Biological material will be labelled with the COPP-IMM study number and date of sampling. The local researcher will note in the COPP-Castor database that the participant has consented for COPP-IMM study and will note the date of sampling. Castor is a LUMC approved data storage program.

The LUMC COPP / COPP-IMM team ([name], [name], [name], [name]) only has access to the coded data and not to patient-identifiable data.

Only the treating physician from the various participating centers will have access to the source data. This means that during the study, within the LUMC Dr. [name] will have access to both coded and source data. After completion of the study, the key to the code will be safeguarded with the Trialbureau WAKZ, an independent location. The LUMC COPP/COPP-IMM team won't have access to the key to the code when analyzing the collected data.

Biological samples will be stored for 15 years for additional investigations that are related to this study. As soon as the samples are no longer necessary, the material will be destroyed.

12.2 Monitoring and Quality Assurance

MultiCenter: Monitoring in all sites in the Netherlands will be executed by (internal) monitors of the LUMC according to the monitor plan (see **Appendix G**).

12.3 Amendments

Amendments are changes made to the research after approval by the accredited METC has been given. All amendments will be notified to the METC that gave a favourable opinion.

Non-substantial amendments will not be notified to the accredited METC and the competent authority, but will be recorded and filed by the sponsor.

12.4 Annual progress report

The sponsor/investigator will submit a summary of the progress of the trial to the accredited METC once a year. Information will be provided on the date of inclusion of the first subject, numbers of subjects included and numbers of subjects that have completed the trial, serious adverse events/ serious adverse reactions, other problems, and amendments.

12.5 Temporary halt and (prematurely) end of study report

The investigator/sponsor will notify the accredited METC of the end of the study within a period of 8 weeks. The end of the study is defined as the time when the last included patient has completed the follow-up survey at six weeks.

The sponsor will notify the METC immediately of a temporary halt of the study, including the reason of such an action.

In case the study is ended prematurely, the sponsor will notify the accredited METC within 15 days, including the reasons for the premature termination.

Within one year after the end of the study, the investigator/sponsor will submit a final study report with the results of the study, including any publications/abstracts of the study, to the accredited METC.

12.6 Public disclosure and publication policy

The results of this study will be published in peer-reviewed journals, initiated by the sponsor. Temporary results will be published on a dashboard on the website www.covidkids.nl. The investigators of the participating sites will form part of the publishing consortium.

13. STRUCTURED RISK ANALYSIS

As this research does not involve a medicinal product, food product, medical device or other (as described in chapter 6 and 7) this paragraph is not applicable.

15. APPENDICES

APPENDIX A: Data Management Plan

APPENDIX B: Instruction in “Positive language” during procedures, courtesy of Stichting Kind en Ziekenhuis

APPENDIX C: Standard Operating Procedure (SOP) blood collection

APPENDIX D: Questionnaire at 12 weeks follow-up

- Algemene vragenlijst
- Surveys PedsQL
- Surveys PROMIS

APPENDIX E: Flow chart follow up questionnaire after 12 weeks

APPENDIX F: Statement patient data in observational cohort studies in emergency situations and COVID-19

APPENDIX G: Monitor plan

APPENDIX H: Yearly Questionnaire corona vaccination
